## **8.4.2 Pregnancy**

All pregnancies and outcomes of pregnancy should be reported to AstraZeneca except for pregnancy discovered before the study patient has received any IPs.

### **8.4.2.1 Maternal exposure**

If a patient becomes pregnant during the course of the study, the IPs should be discontinued immediately.

Pregnancy itself is not regarded as an AE unless there is a suspicion that the IP under study may have interfered with the effectiveness of a contraceptive medication. Congenital abnormalities or birth defects and spontaneous miscarriages should be reported and handled as SAEs. Elective abortions without complications should not be handled as AEs. The outcome of all pregnancies (spontaneous miscarriage, elective termination, ectopic pregnancy, normal birth, or congenital abnormality) should be followed up and documented even if the patient was discontinued from the study.

If any pregnancy occurs in the course of the study, then the Investigator or other site personnel informs the appropriate AstraZeneca representatives within 1 day (ie, immediately but **no later than 24 hours**) of when he/she becomes aware of it.

The designated AstraZeneca representative works with the Investigator to ensure that all relevant information is provided to the AstraZeneca Patient Safety data entry site within 1 to 5 calendar days for SAEs (see Section 8.4.1) and within 30 days for all other pregnancies.

The same timelines apply when outcome information is available.

#### **8.4.2.2 Paternal exposure**

Male patients should refrain from fathering a child or donating sperm during the study and for 90 days following the last dose of IP. Please follow the local prescribing information relating to contraception and the time limit for such precautions.

Pregnancy of the patient's partners is not considered to be an AE. However, the outcome of all pregnancies (spontaneous miscarriage, elective termination, ectopic pregnancy, normal birth, or congenital abnormality) occurring from the date of the first dose until 90 days after the last dose of IP should, if possible, be followed up and documented.

Where a report of pregnancy is received, prior to obtaining information about the pregnancy, the Investigator must obtain the consent of the patient's partner. Therefore, the local study team should adopt the generic ICF template in line with local procedures and submit it to the relevant Independent Ethics Committees (IECs)/Institutional Review Boards (IRBs) prior to use.

#### **8.4.3 Overdose**

Use of IP (durvalumab or olaparib) in doses in excess of that specified in the protocol is considered to be an overdose. There is currently no specific treatment in the event of overdose with durvalumab or olaparib, and possible symptoms of overdose are not established for these IPs.

- An overdose with associated AEs will be recorded as the AE diagnosis or symptoms in the relevant AE modules of the eCRF and on the Overdose eCRF module.
- An overdose without associated symptoms will only be reported in the Overdose eCRF module.

If an overdose on an AstraZeneca IP occurs in the course of the study, then the Investigator or other site personnel will inform appropriate AstraZeneca representatives immediately or **no later than 24 hours** of when he/she becomes aware of it.

The designated AstraZeneca representative will work with the Investigator to ensure that all relevant information is provided to the AstraZeneca Patient Safety data entry site.

For overdoses associated with an SAE, the standard reporting timelines apply (see Section 8.4.1). For other overdoses, reporting must occur within 30 days.

#### **8.4.4 Medication error**

If a medication error occurs in the course of the study, then the Investigator or other site personnel informs the appropriate AstraZeneca representatives within 1 day (ie, immediately but no later than 24 hours) of when he/she becomes aware of it.

The designated AstraZeneca representative works with the Investigator to ensure that all relevant information is completed within 1 or 5 calendar days if there is an SAE associated with the medication error (see Section 8.3.2) and within 30 days for all other medication errors.

The definition of a medication error can be found in [Appendix B](#).

#### **8.4.5 Management of IP-related toxicities and dose reductions**

The following general guidance should be followed for management of toxicities:

- Treat each of the toxicities with maximum supportive care (including holding the agent suspected of causing the toxicity if required).
- If the symptoms promptly resolve with supportive care, consideration should be given to continuing the same dose of the assigned IP along with appropriate continuing supportive care. If medically appropriate, dose modifications are permitted.
- All dose modifications should be documented with clear reasoning and documentation of the approach taken.
- Patients should be thoroughly evaluated to rule out any alternative etiology (eg, disease progression, concomitant medications, or infections).

- In the absence of a clear alternative etiology, all events should be considered potentially immune related, and the Dosing Modification and Toxicity Management Guidelines (see Section 8.4.5.1 for durvalumab and Section 8.4.5.2 for olaparib) should be followed.
- In the event that durvalumab is discontinued or delayed as part of the Dosing Modification and Toxicity Management Guidelines (Section 8.4.5), olaparib/placebo may still be administered as scheduled.
- In the event that olaparib or placebo is discontinued due to treatment-related toxicity, durvalumab may continue at the Investigator's discretion when toxicity resolves to at least Grade 2 or less. Note: If the Investigator feels that a patient is ready to restart treatment prior to the toxicity resolving to Grade 2 or less, AstraZeneca should be consulted for an exception to this rule.

If unsure how to manage a patient, please contact the Study Physician at AstraZeneca to discuss individual cases. All toxicities will be graded according to NCI CTCAE version 4.03.

#### **8.4.5.1 Durvalumab**

Comprehensive toxicity management guidelines (TMG) have been developed to assist investigators with the recognition and management of toxicities associated with the use of the immune-checkpoint inhibitors durvalumab [Medi4736] (PD-L1 inhibitor). Given the similar underlying mechanisms of toxicities observed with these two compounds, these guidelines are applicable to the management of patients receiving either drug as monotherapy or in combination. Additionally, these guidelines are applicable when either drug is used alone or in combination and is administered concurrently or sequentially with other anti-cancer drugs (i.e. antineoplastic chemotherapy, targeted agents), as part of a protocol specific treatment regimen.

The TMGs provide information for the management of immune-mediated reactions, infusion-related reactions, and non-immune mediated reactions that may be observed with checkpoint inhibitor monotherapy or combination checkpoint inhibitor regimens, with specific instructions for dose modifications (including discontinuations) and treatment interventions. Investigators are advised however to use local practice guidelines and consult local references for the management of toxicities observed with other cancer treatment <<Insert relevant section which describes a non-IO regimen, if applicable>>. The most current version of the TMGs entitled "Dosing Modification and Toxicity Management Guidelines for Immune-Mediated, Infusion-Related, and Non-Immune Mediated Reactions (MEDI4736) Monotherapy is provided to the investigative site as an Annex document and is maintained within the Site

Master File. In addition, a version of the current Dosing Modification and Toxicity Management Guidelines is available through the following link: <https://tmg.azirae.com>. Please contact the clinical study associate for information on how to gain access to this website

Patients should be thoroughly evaluated, and appropriate efforts should be made to rule out neoplastic, infectious, metabolic, toxin, or other etiologic causes of the imAE. Serologic, immunologic, and histologic (biopsy) data, as appropriate, should be used to support an imAE diagnosis. In the absence of a clear alternative etiology, events should be considered potentially immune related.

In addition, there are certain circumstances in which durvalumab should be permanently discontinued (see Section 7.1 of this protocol and the Dosing Modification and Toxicity Management Guidelines).

Following the first dose of the IP, subsequent administration of durvalumab can be modified based on toxicities observed as described in the Dosing Modification and Toxicity Management Guidelines. These guidelines have been prepared by the Sponsor to assist the Investigator in the exercise of his/her clinical judgment in treating these types of toxicities. These guidelines apply to AEs considered causally related to durvalumab monotherapy regimen by the reporting Investigator.

**Dose reductions are not permitted.** In case of doubt, the Investigator should consult with the Study Physician.

#### **8.4.5.2 Olaparib**

Any toxicity observed during the course of the study could be managed by interruption of the dose of study treatment or dose reductions. Repeat dose interruptions are allowed as required, for a maximum of 4 weeks on each occasion. If the interruption is any longer, the study team must be informed. For patients with  $\text{CrCl} \geq 51$  mL/min dosed with 300 mg BID, study treatment can be dose reduced to 250 mg BID as a first step and to 200 mg BID as a second step. If the reduced dose of 200 mg BID is not tolerable, no further dose reduction is allowed and study treatment should be discontinued.

For patients with  $\text{CrCl} \geq 31$  mL/min but  $< 51$  mL/min dosed with 200 mg BID, study treatment can be reduced to 150 mg BID as a first step and to 100 mg BID as a second step. If the reduced dose of 100 mg BID is not tolerable, no further dose reduction is allowed, and study treatment should be discontinued.

Dose re-escalation is permitted in the study at the discretion of the Investigator.

**Table 12 Management of anemia**

Hemoglobin (Hb)	Action to be taken
Hb <10 but ≥8 g/dL (CTCAE Grade 2)	
Give appropriate supportive treatment and investigate causality.
 
Investigator judgment to continue study treatment with supportive treatment (eg, transfusion) or interrupt dose for a maximum of 4 weeks.
 
For patients with CrCl ≥51 mL/min dosed with 300 mg twice daily: If repeat Hb <10 but ≥8 g/dL, interrupt dose (for maximum of 4 weeks) until Hb ≥10 g/dL, and upon recovery, dose reduction to 250 mg twice daily as a first step and to 200 mg twice daily as a second step may be considered.
 
For patients with CrCl ≥31 mL/min but <51 mL/min dosed with 200 mg twice daily: If repeat Hb <10 but ≥8 g/dL, interrupt dose (for maximum of 4 weeks) until Hb ≥10 g/dL, and upon recovery, dose reduction to 150 mg twice daily as a first step and to 100 mg twice daily as a second step may be considered.

Hb <8 g/dL (CTCAE Grade 3)	
Give appropriate supportive treatment (eg, transfusion) and investigate causality.
 
For patients with CrCl ≥51 mL/min dosed with 300 mg twice daily: Interrupt study treatment for a maximum of 4 weeks until improvement to Hb ≥10 g/dL, and upon recovery, reduce dose to 250 mg twice daily as a first step and to 200 mg twice daily as a second step in the case of repeat Hb decrease.
 
For patients with CrCl ≥31 mL/min but <51 mL/min dosed with 200 mg twice daily: If repeat Hb <10 but ≥8 g/dL, interrupt dose (for maximum of 4 weeks) until Hb ≥10 g/dL, and upon recovery, reduce dose to 150 mg twice daily as a first step and to 100 mg twice daily as a second step may be considered.

Common treatable causes of anemia (eg, iron, vitamin B12, or folate deficiencies and hypothyroidism) should be investigated and appropriately managed. In some cases, management of anemia may require blood transfusions. For cases where patients develop prolonged hematological toxicity (≥2-week interruption/delay in study treatment due to CTCAE Grade 3 or worse anemia and/or development of blood transfusion dependence), refer to [Management of prolonged hematological toxicities while on study treatment](#).

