**Table 13 Management of neutropenia, leukopenia and thrombocytopenia**

Toxicity	Study treatment dose adjustment
CTCAE Grade 1-2	Investigator judgment to continue treatment or if to interrupt study treatment; this should be for a maximum of 4 weeks; give appropriate supportive treatment and causality investigation.
CTCAE Grade 3-4	
Dose interruption until recovered to CTCAE Grade 1 or better for a maximum of 4 weeks.
 
For patients with CrCl <math>\geq 51</math> mL/min dosed with 300 mg twice daily: If repeat CTCAE Grade 3-4 occurrence, reduce study treatment dose to 250 mg twice daily as a first step and 200 mg twice daily as a second step.
 
For patients with CrCl <math>\geq 31</math> mL/min but <math>< 51</math> mL/min dosed with 200 mg twice daily: If repeat CTCAE Grade 3-4 occurrence, reduce study treatment dose to 150 mg twice daily as a first step and 100 mg twice daily as a second step.

AE of neutropenia and leukopenia should be managed as deemed appropriate by the Investigator with close follow-up and interruption of study drug if CTCAE Grade 3 or worse neutropenia occurs.

Primary prophylaxis with granulocyte colony-stimulating factor (G-CSF) is not recommended; however, if a patient develops febrile neutropenia, study treatment should be stopped and appropriate management including G-CSF should be given according to local hospital guidelines. Please note that G-CSF should not be used within at least 24 hours (7 days for pegylated G-CSF) of the last dose of study treatment unless absolutely necessary.

Platelet transfusions, if indicated, should be done according to local hospital guidelines.

For cases where patients develop prolonged hematological toxicity ( $\geq 2$ -week interruption/delay in study treatment due to CTCAE Grade 3 or worse), refer to [Management of prolonged hematological toxicities while on study treatment](#).

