**Management of prolonged hematological toxicities while on study treatment**

If a patient develops prolonged hematological toxicity such as:

- $\geq 2$ -week interruption/delay in study treatment due to CTCAE Grade 3 or worse anemia and/or development of blood transfusion dependence
- $\geq 2$ -week interruption/delay in study treatment due to CTCAE Grade 3 or worse neutropenia ( $ANC < 1 \times 10^9/L$ )
- $\geq 2$ -week interruption/delay in study treatment due to CTCAE Grade 3 or worse thrombocytopenia and/or development of platelet transfusion dependence ( $platelets < 50 \times 10^9/L$ )

Check weekly differential blood counts including reticulocytes and peripheral blood smear. If any blood parameters remain clinically abnormal after 4 weeks of dose interruption, the patient should be referred to a hematologist for further investigations. Bone marrow analysis and/or blood cytogenetic analysis should be considered at this stage according to standard hematological practice. Auto-immune causes of hematologic toxicities should be considered in the differential diagnosis. Study treatment should be discontinued if blood counts do not recover to CTCAE Grade 1 or better within 4 weeks of dose interruption.

Development of a confirmed MDS or other clonal blood disorder should be reported as an SAE and full reports must be provided by the Investigator to the AstraZeneca representative. Study treatment should be discontinued if patient's diagnosis of MDS and/or AML is confirmed.

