### **Management of non-hematological toxicity**

If this is suspected to be immune mediated, refer to the durvalumab Dosing Modification and Toxicity Management Guidelines (see Section 8.4.5.1). The most current version of the Toxicity Management Guidelines is also available through the following link: <https://tmg.azirae.com>. In addition, a version of the current Toxicity Management Guidelines is maintained within the Site Master File. Please contact your clinical trial associate for information on how to gain access to this website.

Repeat dose interruptions are allowed as required, for a maximum of 4 weeks on each occasion. If the interruption is any longer than this, the Study Monitor must be informed. Where toxicity re-occurs following re-challenge with study treatment, and where further dose interruptions are considered inadequate for management of toxicity, then the patient should be considered for dose reduction or must permanently discontinue study treatment.

For patients with  $CrCl \geq 51$  mL/min dosed with 300 mg BID, study treatment can be dose reduced to 250 mg BID as a first step and to 200 mg BID as a second step. For patients with  $CrCl \geq 31$  mL/min but  $< 51$  mL/min and dosed with 200 mg BID, study treatment can

be dose reduced to 150 mg BID as a first step and to 100 mg as a second step. Treatment must be interrupted if any NCI-CTCAE Grade 3 or 4 AE occurs, which the Investigator considers to be related to the administration of study treatment.

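### Table 12: at hemoglobin below 8 g/dL, the entry for patients on olaparib 200 mg twice daily carries the Grade 2 trigger, so the mandatory interruption and dose reduction are missing for them

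*Protocol*

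**What the plan says.** Section 8.4.5.2 and Table 12 divide patients by starting dose: 300 mg twice daily for creatinine clearance of at least 51 mL/min, and 200 mg twice daily for clearance of at least 31 but below 51 mL/min.

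The Grade 3 row of Table 12 covers hemoglobin below 8 g/dL. It opens, for both groups, with supportive treatment (transfusion is the example) and a search for the cause. It then separates them:

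- **300 mg group:** "Interrupt study treatment for a maximum of 4 weeks until improvement to Hb ≥10 g/dL, and upon recovery, reduce dose to" 250 mg, then 200 mg if hemoglobin falls again. No further condition is attached.
- **200 mg group:** "interrupt dose (for maximum of 4 weeks) until Hb ≥10 g/dL, and upon recovery, reduce dose to" 150 mg, then 100 mg. This applies only if a repeat hemoglobin is below 10 but at least 8 g/dL, and the sentence closes by saying that the step may be considered.

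For the other cytopenias, the Grade 3-4 row of Table 13 has one interruption rule for all patients: "Dose interruption until recovered to CTCAE Grade 1 or better for a maximum of 4 weeks".

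**The concern.** The trigger in the 200 mg entry belongs to the Grade 2 row. A patient whose hemoglobin has just been measured below 8 g/dL does not meet it. Taken at its word, the table orders interruption for a 200 mg patient with a repeat hemoglobin of 9 g/dL (Grade 2 row) but gives no such order for one at 7 g/dL. The rule is weaker at the worse value, and only in the group with impaired renal function.

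The closing words add a second problem: the sentence begins as an instruction to reduce the dose and ends as an option.

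The stake is consistent safety management. At the same hemoglobin, one dose group has a mandatory step and the other is left to site judgment. Anemia is a listed olaparib effect (Section 2.3.3.2), and the 200 mg group is a planned part of the population: clearance below 60 mL/min is one of the criteria for platinum ineligibility, and the entry floor is 31 mL/min (Section 5.1).

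**Working it through.** This is a comparison of text; no sample size, power or alpha figure is involved.

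**Step 1. The four dose-group entries in Table 12 (2 rows × 2 groups).**

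| Row | Group | Condition for interruption | Dose reduction | Fits its row? |
|---|---|---|---|---|
| Grade 2: 8 ≤ Hb < 10 | 300 mg | repeat Hb < 10 but ≥ 8 | optional, 250 then 200 mg | yes |
| Grade 2: 8 ≤ Hb < 10 | 200 mg | repeat Hb < 10 but ≥ 8 | optional, 150 then 100 mg | yes |
| Grade 3: Hb < 8 | 300 mg | none beyond the row heading | ordered, 250 then 200 mg | yes |
| Grade 3: Hb < 8 | 200 mg | repeat Hb < 10 but ≥ 8 | mixed wording, 150 then 100 mg | **no** |

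Three of four entries fit. In the fourth, the row covers Hb < 8 and the condition covers 8 ≤ Hb < 10. The two ranges do not overlap.

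**Step 2. Where the entry came from.** It is almost identical to the Grade 2 entry for the same group. The phrase introducing the reduction was changed to an instruction, while the trigger and the optional ending were left in place. The sentence is complete and has its own dose steps, so it does not look like damage from PDF conversion.

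**Step 3. Whether a softer rule was intended.** Nothing in the protocol argues for one. Table 13 orders interruption at Grade 3-4 without a renal split and gives both groups the same trigger for reduction, a repeat Grade 3-4 event.

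**Step 4. Whether another rule fills the gap.**

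- Section 8.4.5.2, general text: "Any toxicity observed during the course of the study could be managed by interruption of the dose of study treatment or dose reductions". Permissive.
- Section 8.4.5: "Treat each of the toxicities with maximum supportive care (including holding the agent suspected of causing the toxicity if required". Also permissive.
- Table 14: gives the 150 mg and 100 mg levels but no hemoglobin trigger.
- Prolonged hematological toxicity: applies after at least 2 weeks of "interruption/delay in study treatment due to CTCAE Grade 3 or worse anemia and/or development of blood transfusion dependence". Apart from transfusion dependence, it presupposes that someone has already interrupted treatment. Its discontinuation rule runs from 4 weeks of interruption, so that clock does not start otherwise.
- Non-hematological toxicity: "Treatment must be interrupted if any NCI-CTCAE Grade 3 or 4 AE occurs". This is mandatory, but it stands under the wrong heading for anemia, covers only events the investigator judges related, and gives neither a recovery threshold of 10 g/dL nor a required reduction. In addition, Section 8.3.7 restricts adverse event reporting of scheduled laboratory deterioration without symptoms to values that meet seriousness criteria or cause discontinuation, so a symptom-free hemoglobin below 8 g/dL may not be recorded as an event at all.

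None of these clearly orders interruption followed by reduction at hemoglobin below 8 g/dL in the 200 mg group.

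**The case against.** The strongest reply is that the trigger can be read as a re-measured value. A patient below 8 g/dL is transfused as the row directs, is measured again at 8 to below 10, and then must interrupt until 10 g/dL. That reading is possible, but such a value already falls under the Grade 2 row. The first reading below 8, and a repeat still below 8, remain without an order.

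Second, the non-hematological sentence refers to any Grade 3 or 4 event. Read broadly, it would make interruption mandatory for related anemia. Even then, the recovery threshold and the reduction step are missing.

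Third, the slip is visible. The neighboring 300 mg entry shows what was meant, the prolonged-toxicity text assumes that Grade 3 anemia leads to interruption, and sites may call the study physician. Many investigators would interrupt anyway. This limits the practical effect; it does not make the cell correct.

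Fourth, Table 13 orders reduction only on a repeat event, so it supports equal handling and interruption, not reduction after a first event. That is right, and it is used here only for those two points.

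Fifth, on timing, the current version is dated 9 July 2021 and the synopsis estimated the last patient completed in Q2 2021, so few patients might still be on treatment. Actual status is not given, and Section 4.4.1 allows treatment to continue past the final data cutoff.

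**Conclusion.** The concern holds. The Grade 3 anemia entry for the 200 mg group is wrong as written, and the mandatory interruption and reduction given to the 300 mg group are absent for it. This is a drafting error carried over from the row above, not a deliberate choice of a weaker rule.

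Its extent in the text is 1 of 4 entries. The number of patients affected cannot be derived: the share starting at 200 mg is not stated, and the toxicity figures quoted for the combination come from other populations and differ widely (39.5% Grade 3 or higher anemia in small cell lung cancer, Section 2.3.4; no Grade 3 to 4 toxicity in the earlier combination study, Section 4.3.2). The consequence is confined to safety management.

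The conclusion assumes that sites apply the table as printed and that the non-hematological rule is confined to its heading. If that rule is read broadly, what is missing narrows to the recovery threshold and the dose reduction.

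**What to change.** In the row for hemoglobin below 8 g/dL, replace the 200 mg entry with the 300 mg wording, "Interrupt study treatment for a maximum of 4 weeks until improvement to Hb ≥10 g/dL, and upon recovery, reduce dose to", followed by 150 mg twice daily as the first step and 100 mg twice daily as the second if hemoglobin falls again. Delete from this cell the condition on a repeat value of 8 to below 10 g/dL and the closing words that make the step optional. The 150 mg and 100 mg levels match Table 14, and no other entry in Table 12 needs to change.

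The cost is amendment wording for one table cell and a notification to sites.
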